8.4.5 Study Procedures and Assessments

Study procedures and assessments are as described in Section 8.3.4 Study Procedures and Assessments

8.4.6 Unscheduled Visits

Unscheduled visits are described in Section 8.1.5 Unscheduled Visits.

8.4.7 Early Termination

Early termination is described in Section 8.1.6 Early Termination.

9. Mechanistic Assays

Planned and potential mechanistic assays for this study are noted below. Blood drawn from participants for mechanistic and clinical blood draws may not exceed NIH blood draw limits (550mL over 8 weeks).

Antibody assays: Antibody levels will be tested at each time point to test for IgG and IgM responses against SARS-CoV-2 spike, receptor binding domain, and nucleocapsid proteins using standardized ELISAs or comparable assays from the

NIAID-VRC, Seronet, or one of the ACE Centers. Additional assays testing for antibody responses against variants or providing epitope specificity, such as through on the University of Texas Southwestern or Stanford arrays [66], may be tested if resources are available. Assays to test for anti-cytokine, autoantibody, anti-adenoviral, and anti-RNA responses may also be tested by the aforementioned combination arrays, ELISAs or a combination of these. Finally, novel assays for antibodies may also be included, as possible. For example, the [name] laboratory (Yale) is using a novel Rapid Extracellular Antigen Profiling (REAP) assay to assess 2,770 extracellular and secreted proteins which have been informative in post-COVID infection [67]. Serum will be used for these assays.

Neutralizing assays: Assays will also be performed to see whether neutralizing antibodies are produced in autoimmune disease participants after additional vaccine administrations. Using the microneutralization assays by plaque reduction in use at the NIAID-VRC, Seronet or at an ACE Center, presence/absence and titer of neutralization will be recorded for each sample. Alternatively, pseudoneutralization assays, where the spike antigen is transfected into a lentiviral vector-based assay could be used as a surrogate. Another option would be the competition ELISA-based surrogate virus neutralization assay (sVNT) for rapid screening of all samples; however, this assay is not as useful for lower concentration neutralization and may not be ideal for autoimmune disease patient samples. Assays will follow the published literature [68]. Serum will be used for these assays.

Antigen-specific T cell responses and T cell repertoires: Autoimmune disease patients, especially those on BCDTs, may have undetectable SARS-CoV-2 antibodies but still mount effective T cell responses against the virus. Using T cell assays in place in the [name], [name], or NIAID labs, briefly PBMCs from each individual sample will be stimulated with SARS-CoV-2 spike protein, other SARS-CoV-2 antigens, positive (PMA) and negative controls, followed by readouts such as IFN gamma ELISPOT [69] or by CD4+ interferon gamma and/or Interleukin-2 (IL-2) and/or Tumor Necrosis Factor alpha (TNF- α) and/or CD40 Ligand (CD40L) secretion/expression by intracellular staining [70]. Please see the ACV01 Lab Manual for more information. T cell epitope mapping and TCR utilization assays may be performed in future use assays. Frozen PBMCs will be used for these assays.

Antigen-specific memory B cell responses and B cell repertoires: In addition to antibodies and T cell mediated immunity, memory B cell responses will also be assessed. Peripheral blood mononuclear cells (PBMCs) will be stimulated with SARS-CoV-2 spike or receptor binding domain and cells assessed for antibody production by ELISPOT. Alternatively, after discussion with the ACE Network investigators, whole blood stimulations with spike antigens may be performed with each blood draw with stabilization to allow the evaluation of B cell and T cell responses post-vaccination as has been performed for COVID-19 infection [71]. From an immunological standpoint, and in addition to overall profiling, detailed studies of antigen-specific B cell responses will be studied in order to understand: a) the cellular compartments in which SARS-CoV-2-specific B cell memory resides; b) its quality, magnitude and distribution within the population; c) its provenance (whether from early or late cellular precursors); and d) its concordance or conversely, uncoupling from serological responses. This approach would enable the group to differentiate between different types of long-term memory responses, including long-term serological memory (dependent on the generation of long-lived plasma cells (LLPC); and cellular memory (B cell memory with or without serological memory). Additional B cell repertoire sequencing may be performed in a subset of patients as well. Frozen PBMCs, or whole blood, will be used for these assays. [name] has developed all the assays for SARS-CoV-2-specific B cell characterization and could be involved in performing these studies with ACV01 samples.

Immunophenotyping and Immune cell population profiling over time: In addition to the above assessments of antigen-specific B and T cell responses, additional immunophenotyping of samples will be performed, at least on a subset of individuals and time points, to determine cell populations that correlate with adequate vaccination responses after additional study vaccine dose administration, either with an mRNA vaccine, a vector-based COVID-19 vaccine, or a protein-based COVID-19 vaccine compared to inadequate responders. Deep immunophenotyping will be performed using the standard panels of the NIAID HICPs by CyTOF or high dimensional flow cytometry as performed by one of the ACE Centers [72, 73]. Stabilized whole blood or PBMCs will be used for these assays. Please see the Lab Manual for additional details.

Gene expression profiling, soluble mediators, autoantibody assessments, and individual hypothesis testing: Several ACE Centers have specific hypotheses that they would like to test with this unique participant collection to determine whether specific immune cell types or pathways associate with neutralizing SARS-CoV-2 responses after vaccination. A

few examples are listed here and others will use the stored biospecimens outlined below. Through work in SLE with influenza and varicella (Zostavax) vaccination, ACE investigators have found that individuals with poor vaccine responses have a higher baseline IFN response [74, 75]. Other work has shown that individuals with increased numbers of CD86 positive naïve B cells, or activated CD11b+ monocytes (or both) are at higher risk of disease flare within the next 4-6 weeks [76]. Increased numbers of CD319+ T cells are found in systemic sclerosis patients compared to controls [77], and can be assessed across autoimmune diseases in this cohort and tested for association with impaired vaccine responses. RNA will be isolated from PAXgene tubes and transcript profiles determined by RNAseq. Module expression will be determined as per the [name] group and modules assessed for association with impaired vaccination responses [78]. Soluble mediator levels of cytokines, chemokines, and soluble receptors will be tested in plasma as outlined by the [name] group [79]. Immunophenotyping data will be used from above to test other hypotheses [78]. Autoantibody profiling, related to the individual autoimmune diseases and with a broader coverage such as an autoantigen array, will be done at each visit to determine effects of an additional study vaccine dose on autoantibody production. Specific questions about changes in autoantibody concentration, isotypes, avidity, new specificities, and epitope expansion could be addressed, as funding allows.

scRNAseq, CITE-seq, scATAC-seq (TEA-Seq): Finally, in another subset analysis, smaller groups of participants on similar background meds who do and do not respond to an additional study vaccine dose will be tested by single cell technologies to generate additional hypotheses regarding the cell types, cell subsets, and immune cell pathways associated with impaired vaccination responses within and across autoimmune diseases. These assays will use frozen PBMCs (or stabilized whole blood) and will use the approaches in standard use within one of the ACE Network Centers.

Together, the data assembled through these mechanistic studies will inform the community about the mechanisms of vaccine response, and non-response, in autoimmune disease patients, as well as potentially in others taking similar medications. Information may also be uncovered regarding autoimmune disease pathogenesis, predictors of vaccine response, and autoimmune disease flare.

Background IS Medication Testing: A critical part of this study is to discover if withholding cohort-defining IS medications influences response to the additional vaccine dose. In order to determine if there is a correlation between IS medication level in the blood and vaccine response, a whole blood specimen will be collected at the Baseline/Week 0 visit for all participants in Cohorts A (MMF/MPA) and B (MTX). If the primary endpoint analysis yields no quantifiable difference between treatment arms withholding IS medication and those continuing their medication in Cohort A (MMF/MPA) and Cohort B (MTX), the Baseline whole blood and serum specimens will be tested to gain additional insight into a relationship between medication blood levels and vaccine response.

Optional Site-specific Sub-studies: The mechanistic assays noted above represent a small portion of the research that can be completed on autoimmune patients receiving an additional COVID-19 vaccine dose. This study presents a unique opportunity to collect data during a critical time in our vaccine response timeline. Individual site investigators may choose to collect additional optional specimens from Baseline/Week 0 to Week 4 to complete mechanistic analysis of their own. All optional mechanistic specimen sub-studies will be detailed in site-specific informed consent forms.

Optional Week 1 Pediatric Specimen Collection: Pediatric participants may choose to participate in an optional specimen collection during the Week 1 Vaccine Diary Review visit (window: Day 7-14). Procedures for this visit are outlined in Section 20.1 Schedules of Events.

10. Biospecimen Storage

The ACE Network investigators will also discuss and prioritize other assays to be performed on the longitudinal samples from this autoimmune disease COVID vaccination trial. To facilitate these future studies, the following biospecimens will be collected at participating sites, processed and stored at the Oklahoma Medical Research Foundation (OMRF) College of American Pathologists (CAP)-certified Biorepository. These biospecimens include: serum, plasma, peripheral blood mononuclear cells, RNA isolated from PAX gene tubes, and DNA isolated from buffy coats. Individuals will be asked to provide consent for genetic studies and to have data, including genetic and gene expression, stored in an NIH-approved public database. Individuals will be able to opt out of genetic testing based upon their preference. Samples will be used within the ACE Network or by outside investigators with compelling questions who collaborate with one of the ACE

Network investigators. Samples will be stored for up to 4 years after the completion of the trial (or for longer in an ACE Network Biorepository or other biorepository approved by NIAID DAIT and the ACE Network. If the NIAID ACE Network were to disband, then NIAID DAIT will work with the housing institution for the final dispensation of the samples.

11. Criteria for Participant and Study Completion and Premature Study Termination

11.1 Participant Completion

Participation will be considered to be complete when the Week 48 visit of the participant's last stage of participation is complete.

11.2 Participant Stopping Rules and Withdrawal Criteria

Participants may be prematurely terminated from the study for the following reasons:

1. The participant and/or legal guardian elects to withdraw consent from all future study activities, including follow-up.
2. The participant is "lost to follow-up" (i.e., no further follow-up is possible because attempts to reestablish contact with the participant have failed).
3. The participant dies.
4. The Investigator no longer believes participation is in the best interest of the participant.
5. The participant does not receive the additional vaccine dose at Baseline/Week 0 or S2 Baseline/Week 0 (new recruits only) for any reason, including the criteria listed in Section 8.1.3 Baseline (Week 0/Day 1) Visit or at Section 8.2.4 Baseline (Week 0/Day 1) Visit, respectively.
6. The participant receives a SARS-CoV-2 vaccine outside of the study.

11.3 Participant Replacement

Participants who withdraw or are withdrawn will not be replaced if they have received a vaccine dose at a given stage of the study. If a Stage 1 or newly recruited Stage 2 participant is randomized or allocated to a study arm but does not receive the vaccine, the participant will be withdrawn and will not be counted toward the total accrual objective. If a Stage 2 rollover patient is allocated to a study arm but does not receive the vaccine, the participant will continue on their previous Schedule of Events and will not be counted toward the Stage 2 accrual objective. Additional participants will be consented and randomized/allocated to achieve the accrual objective(s).

11.4 Follow-up after Early Study Withdrawal

Participants who prematurely withdraw (without withdrawing consent) or who are withdrawn may be asked to complete a final phone visit to assess any AEs and concomitant medications as applicable depending on when they are withdrawn relative to the visit schedule. Participants who are withdrawn from the study prior to receipt of study treatment will not be followed after their last completed study visit. Monitoring of a pregnant participant will continue until the conclusion of the pregnancy.

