6.7 Toxicity Prevention and Management

Participants will receive investigational agents in facilities where the investigative team is familiar and practiced in the treatment and care of participants with systemic autoimmune diseases and complications associated with those disorders and the associated treatments. Vaccinations will also only be given by personnel trained in recognizing and managing treatment of systemic allergic reactions and in areas equipped with the necessary medications and supplies to treat systemic allergic reactions. Participants who are experiencing a disease flare at Baseline/Week 0, or who meet any of the conditions listed in Section 8.1.3 Baseline (Week 0/Day 1) Visit will not proceed with vaccination. Refer to Section 5.1.1.1 Allergic Reactions and Anaphylaxis and Section 7.4 Rescue Medications.

7. Other Medications

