8.1.3 Baseline (Week 0/Day 1) Visit

Eligible participants who meet all inclusion criteria and none of the exclusion criteria will proceed with visits and assessments according to Section 20.1 Schedule of Events. Eligible participants will be assessed for disease activity and SARS-CoV-2 infection at the Baseline/Week 0 visit, prior to receipt of an additional homologous vaccine dose. Prior to administering the additional homologous vaccine dose at the Baseline visit, the site will confirm the participant meets vaccine eligibility per the criteria below:

- No increase to the permitted concomitant medications in participants in Cohorts A and B between Randomization and Baseline/Week 0.
- No B-cell depletion infusions or changes in permitted concomitant medications in participants in Cohort C between allocation and Baseline/Week 0.
- No clinically active disease (including myocarditis or pericarditis) at Baseline/Week 0 resulting in an increase/addition of IS medications. For participants with MS, no suggestion of a MS relapse per the investigator.
- No active myocarditis or pericarditis based on review of clinical symptoms.
- No positive molecular COVID-19 test at Baseline/Week 0.
- No increase in oral, intramuscular, or intravenous steroids within 14 days of Baseline/Week 0.

If the vaccine cannot be administered at the Baseline/Week 0 visit, it must be administered during the following 2-3 days. Vaccine eligibility will be confirmed prior to administration of the vaccine. **Administration of the additional homologous vaccine dose must occur within 28 days of the Screening visit.**

If a participant is not eligible to receive the additional homologous vaccine dose at Baseline/Week 0, he/she will be terminated from the study. The participant may rescreen under a new participant ID after 30 days from the determination of vaccine ineligibility. Participants who were randomized to withhold cohort-defining IS medications before the Baseline visit and who are not eligible to receive an additional homologous vaccine dose at that visit, may restart their IS medications immediately. The participant will be replaced.

See Section 8.1.4 Study Procedures and Assessments for more information on individual clinical and research assessments.

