12.4.2 Increase in Autoimmune Disease Activity

Any increase in autoimmune disease activity (flare/relapse) for the participant's qualifying autoimmune disease will not be reported as an AE. These events will be collected and reported on the disease-specific assessment eCRFs. (Section 8.1.4.2 Disease-Specific Assessments).

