12.8.2.2.2 Ad Hoc DSMB Reviews for Pediatric Participants

In addition to the pre-scheduled data reviews and planned safety monitoring, the DSMB may be called upon for ad hoc reviews. The DSMB will review any event that potentially impacts safety at the request of the protocol chair or DAIT/NIAID. Any of the following events will trigger an ad hoc DSMB Safety Review:

- Death related to vaccine
- Life-threatening AE (Grade 4) related to vaccine
- Permanent or severe disability related to vaccine
- Occurrence of a Grade 3 or higher, vaccine-related SAE of the same type in 3 or more of the study participants who have received a study treatment. *Note: Only SAEs occurring between Day 1 and the Week 24 study visit will be counted.*
- Occurrence of a Grade 2 or higher myocarditis or pericarditis within 6 weeks of vaccine administration. *Note: the DSMB chair will be notified within 3 business days from when the AESI is reported to DAIT/NIAID.*
- Occurrence of severe flare or relapse after an additional homologous COVID-19 vaccine dose given at Stage 1, defined as within 12 weeks of the Stage Baseline/Week 0 visit (vaccination), in 3 of the first 10 participants or 30% thereafter, defined as follows.
- Occurrence of severe flare or relapse after a subsequent alternative COVID-19 vaccine dose given at Stage 2, defined as within 12 weeks of the Stage 2 Baseline/Week 0 visit (vaccination), in 3 of the first 10 participants or 30% thereafter.

Severe flare or relapse is defined as follows:

- **JIA:**

- a. JADAS10 >17 (polyarthritis, enthesitis-related JIA, and psoriatic arthritis), JADAS10 >13 (for oligoarthritis)
- b. PASI ≥12 (for psoriatic arthritis)
- **Pediatric SLE:** ≥ 6.4 on the SLEDAI-based ACR provisional criteria for global flares in childhood-onset SLE
- **JDM:** Decline in CMAS to <30 or JDM DAS>5
- **POMS:** Clinical relapse meeting either the criteria specified in (a) with investigator determination of relapse or the criteria in (a) **and** (b) below:
 - a. Occurrence of new, recurrent or worsening neurological symptoms attributable to MS, that meet all of the following criteria:
 - v. Appeared or evolved subacutely (over <3 months)
 - vi. Persisting for >24 hours.
 - vii. Cannot be attributed to confounding factors (e.g., fever, infection, injury, poor sleep, adverse reaction to medication)
 - viii. Occur ≥ 30 days after the onset of a prior confirmed relapse.

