13.4 Analysis Plan

13.4.1 Analysis Populations

The following populations will be defined separately for Stage 1 and Stage 2.

Vaccinated population: will be defined as all participants who are randomized or allocated and receive study vaccine in the study. For all endpoints, participants will be evaluated by the actual vaccine received. In Cohorts A and B, participants will be analyzed in subgroups defined by randomized assignment to continue or withhold IS medications in the primary analysis.

Per protocol populations: will be defined as the subgroup of participants in the vaccinated population who adhere to the treatment plan for IS medications defined in Section 7.1.1 Protocol-mandated Medications and have no major protocol deviations or ineligible entry criteria that would impact the vaccine response assessment at Week 4.

Safety population: will be defined as all participants who initiate the treatment plan for IS medications or receive an additional dose of vaccine.

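### Flares during the pre-vaccination medication hold are not assigned to any planned flare summary, and Stage 1 or newly recruited Stage 2 participants who miss vaccination because of active disease are replaced and not followed

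*Protocol*

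**What the plan says.** Withholding versus continuing MMF/MPA or MTX is the only randomised contrast in the trial (Stage 1, Cohorts A and B; Protocol 3.5). The hold begins before vaccination (7.1.1), and Protocol 5.3.1 accepts that it may provoke a flare.

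- **Who is not vaccinated.** Protocol 8.1.3 requires, before the dose, "No clinically active disease (including myocarditis or pericarditis) at Baseline/Week 0 resulting in an increase/addition of IS medications", and no suggested relapse in MS. Protocol 6.7 is wider. It stops vaccination for "Participants who are experiencing a disease flare at Baseline/Week 0, or who meet any of the conditions listed" in 8.1.3.
- **What happens next.** Protocol 8.1.3: "If a participant is not eligible to receive the additional homologous vaccine dose at Baseline/Week 0, he/she will be terminated from the study", and "The participant will be replaced". Sections 8.2.4 and 8.4.4 do the same for newly recruited Stage 2 participants. Under 11.3 they do not count toward accrual. Under 11.4, "Participants who are withdrawn from the study prior to receipt of study treatment will not be followed after their last completed study visit".
- **When counting starts.** The disease-activity endpoints (3.3) concern change after the dose. The severe-flare trigger is "defined as within 12 weeks of the Stage Baseline/Week 0 visit (vaccination") in 12.8.2.2.2, and the adult trigger in 12.8.2.2.1 has the same anchor.
- **Adverse events.** Under 12.4.2, an increase in activity of the "qualifying autoimmune disease will not be reported as an AE". The Grade 3 or higher window between randomisation and vaccination (12.4.1) therefore does not catch it, and SAE collection starts on Day 1.
- **Populations.** The Safety population is "all participants who initiate the treatment plan for IS medications or receive an additional dose of vaccine" (Protocol 13.4.1, SAP 5). The Vaccinated population requires the dose.
- **SAP.** Section 8.3.7 summarises flares by Week 4 without a start date or a named sample. Sections 8.3.7.1 to 8.3.7.11 defer the detail to later versions.

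**The concern.** The randomised intervention starts days before the point from which flares are counted. If stopping MMF/MPA or MTX sets off a flare that needs treatment in that interval, the participant leaves the study, a replacement is recruited, and later follow-up ends. Anything reported on vaccinated participants is then conditioned on a post-randomisation event that the intervention can affect.

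Protocol 1.2.1 presents the trial as a way to find strategies that are safe as well as effective, so readers will use the flare results to judge whether a short hold is safe. A flare proportion that leaves out the early part of the hold would favour the withhold arms.

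**Working it through.** The plan states no figure that depends on this point, so there is none to reproduce.

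**1. Where a hold-period flare could be recorded, and where it would be counted**

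- *Week 0 visit.* Disease activity is assessed before the dose (5.3.1, 8.1.3) and goes on the disease-specific forms (12.4.2). H-SLEDAI, DAS28-CRP and PDAI need not be repeated if Screening was under 10 days earlier (Table 17 footnotes), and Table 20 has a similar waiver for children. Randomisation can be as little as 7 days before Week 0, so the last score may predate the hold.
- *Unscheduled visit (8.1.5).* Available for increased disease activity, with full disease assessments.
- *Early Termination visit.* 8.1.6 says it should be requested on withdrawal. 11.4 says there is no follow-up for those withdrawn before study treatment. The two need reconciling.
- *Disposition (SAP 6.1).* Reasons for not receiving vaccine are tabulated. A reason is not a flare outcome.
- *DSMB listings (12.8.2.1).* Flares are listed, with no start window stated.
- *Flare proportion (SAP 8.3.7).* Start date and sample unstated. It sits among the secondary endpoints, so the rule in SAP 9.1 that safety analyses use the safety sample does not clearly reach it.

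The flare may therefore be recorded, but no planned summary is written to count it.

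**2. Share of the planned hold that precedes vaccination** (days before ÷ total days, from 7.1.1)

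- MMF/MPA: 3 / (3 + 10) = 3/13 = 23%.
- MTX at the minimum hold: 7 / (7 + 7) = 50%.
- MTX at the 21-day cap: 7/21 = 33% to 14/21 = 67%.

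These are shares of days. They do not measure flares or bias.

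**3. Effect on the flare proportion (assumed rates)**

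Let h be the probability of a flare in the hold that prevents vaccination, and f the probability of a flare after vaccination among those vaccinated. Neither is in the documents. Assume h = 2% to 20% and f = 5% to 20%.

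- Risk from the start of the plan: h + (1 − h)f.
- Proportion if the never-vaccinated stay in the denominator uncounted: (1 − h)f.
- The difference is h, whatever the value of f.

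At f = 10%:

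| h | From start of plan | Uncounted |
|---|---|---|
| 2% | 11.8% | 9.8% |
| 10% | 19.0% | 9.0% |
| 20% | 28.0% | 8.0% |

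The withhold-minus-continue difference is then too small by h(withhold) − h(continue). If f = 10% in both plans, h = 10% under withholding and 0% under continuing, the actual risks are 19.0% and 10.0%, while the reported ones are 9.0% and 10.0%.

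**4. How many people this would involve**

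Participants needed to vaccinate N = N / (1 − h). At h = 10%: 60 / 0.90 = 66.7 (about 67) for an Adult Stage 1 arm, and 80 / 0.90 = 88.9 (about 89) for a full 80-participant arm. That is about 7 to 9 never-vaccinated participants per full arm. At h = 2% it is 61.2 and 81.6, so 1 to 2. At h = 20% it is 75 and 100, so 15 to 20.

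**The case against.** The strongest reply is that these flares are not hidden. Week 0, unscheduled and early-termination assessments can record them, the Safety population includes anyone who began the plan, disposition tables give the reason for non-vaccination, and the DSMB sees flares without a start window. All of this stands. A reader might infer that hold-period flares vanish from the safety data altogether, and the documents do not support that. What they leave open is whether a recorded flare enters the flare proportion, and they end follow-up of its outcome.

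A reader might also infer that every participant who flares is lost. That is too broad. Stage 2 rollovers who miss the dose continue on their previous schedule (8.2.4, 8.4.4, 11.3), and 8.1.3 bars only active disease leading to more IS medication or a suggested MS relapse.

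A third inference is that the DSMB trigger must restart at the hold. The Synopsis frames the triggers around events attributable to the vaccine, and the disease-activity objective (2.2.1) concerns the period following the dose. The anchor therefore matches its stated purpose.

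Three further points stand. The eligibility rule applies to continue arms too, so bias needs an excess of flares under withholding, which is plausible but not shown. MTX is a weekly dose, so a hold starting 7 days before vaccination may omit no dose before it. The primary test is single-arm and flare summaries are descriptive, so no formal comparison of flares between plans is specified. These points limit the likely size. They do not tell the analyst where to count a pre-vaccination flare.

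**Conclusion.** The point holds for Stage 1 and for newly recruited Stage 2 participants. A flare in the pre-vaccination hold that prevents vaccination ends follow-up and lies outside the severe-flare trigger and the post-vaccination endpoints. No planned flare summary says that it counts it. If these participants remain in the Safety denominator uncounted, the flare proportion is too low by the share lost, and the withhold-versus-continue difference is too small by the excess share lost under withholding.

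The size is unknown. The 9.0% against 19.0% illustration rests on assumed rates, and the 23% to 67% of hold days cannot be read as a share of flares. In Stage 2 there is no randomised contrast, so the effect there is an understated proportion within arms. The primary antibody test and its power do not depend on this point. It is a gap in specification and follow-up that is cheap to close.

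**What to change.** 1. **SAP.** Alongside the post-vaccination summary, summarise flares from randomisation or allocation (start of the IS plan) in the Safety population by assigned IS plan. Show hold-period flares and never-vaccinated participants separately by plan. For Adult Stage 1, closed on 15 August 2022, use the data already collected. SAP 2 requires a final SAP before database lock, and 8.3.7 is still to be completed.
2. **Protocol, arms still open.** Reconcile 8.1.6 with 11.4. Extend the final phone contact already described in 11.4, which covers adverse events and medications, to record flare status in participants who started the plan but were not vaccinated. Among randomised arms this helps Pediatric Stage 1.
3. **DSMB.** Show hold-period flares by plan in the existing flare listings, and leave the trigger as it is.
4. **Consistency.** Reconcile 6.7 (any flare at Week 0) with 8.1.3 (active disease leading to more IS medication), so that sites apply one rule and the reason for non-vaccination has one meaning.

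The cost is one extra table, a few phone contacts and protocol wording. No dose, hold length or sample size has to change.
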